9.3 Confidentiality and Data privacy

Participant confidentiality and privacy is strictly held in trust by the participating investigator, their staff, and the sponsor(s) and their interventions. This confidentiality is extended to cover testing of biological samples and genetic tests in addition to the clinical information relating to participants. Therefore, the study protocol, documentation, data, and all other information

generated will be held in strict confidence. No information concerning the study or the data will be released to any unauthorized third party without prior written approval of the sponsor.

All research activities will be conducted in as private a setting as possible.

The study monitor, other authorized representatives of the sponsor, representatives of the Institutional Review Board (IRB), or regulatory agencies may inspect all documents and records required to be maintained by the investigator, including but not limited to, medical records (office, clinic, or hospital) and pharmacy records for the participants in this study. The clinical study site will permit access to such records.

The study participant's contact information will be securely stored at each clinical site for internal use during the study. At the end of the study, all records will continue to be kept in a secure location for as long a period as dictated by the reviewing IRB, Institutional policies, or sponsor requirements.

9.4 Study Record Retention

The Principal Investigator and Integra LifeSciences will maintain accurate, complete, and current records relating to participation in this study. If the Principal Investigator wishes to assign the responsibility of maintaining the study files to someone else or move them to another location, he/she should consult with Integra LifeSciences in writing regarding the change. The Principal Investigator will take measures to ensure that these essential documents are not accidentally damaged or destroyed.

Upon study completion, the investigator on one hand and Integra LifeSciences on the other hand will maintain all study records for the minimum time required by the US law and regulation and in accordance with 21 CFR 812, Subpart G.

10 Statistical Considerations

The detailed analyses methods will be described in the Statistical Analyses Plan (SAP).

10.1 Statistical Hypotheses

This is a prospective, single-arm, single center post-market study to capture existing clinical performance data to confirm the continued performance of the GENTRIX® Surgical Matrix. A formal hypothesis does not apply to this study. Subjects from that consecutive series will be included in the study based on the defined inclusion and exclusion criteria.

T-GENVIH-003 study

Confidential

Protocol Version: V1.0 dated 02AUG2023

Page 35 of 41

This document contains proprietary and confidential information of Integra LifeSciences Corporation. Integra's confidential information may not be used, disclosed or reproduced without the prior written consent of Integra LifeSciences Corporation.

Primary Endpoint(s):

The primary endpoint of this prospective study is to determine the incidence of clinically confirmed recurrence of the primary hernia to date, including not previously reported in T-GENVIH-002 study.

Secondary Endpoint(s):

1. Incidence of self-reported recurrence (i.e., bulge) of the primary hernia to date, including not previously reported in T-GENVIH-003 study.
2. Incidence of Surgical Site Occurrences requiring Procedural Intervention (SSOPI) of the primary hernia repair to date, including not previously reported in T-GENVIH-002.
3. Incidence of Surgical Site Occurrences (SSOs) of the primary hernia repair to date (seroma, abscess, dehiscence, hematoma, wound necrosis, ileus, fistula, delayed wound healing), including not previously reported in T-GENVIH-002 study.
4. Incidence of Surgical Site Infections (SSIs) post primary hernia repair to date, including not previously reported in GENVIH-002 study.
5. Incidence of reoperation requirement of the primary hernia repair to date, including not previously reported in GENVIH-002 study.

10.2 Sample Size Determination

Subjects from that consecutive series will be included in the study based on the defined inclusion and exclusion criteria. The planned sample size for this study will be approximately 21 treated subjects.

10.3 Populations for Analyses

Full Analysis Set (FAS): All subjects who enroll in the study, provide informed consent , and receive study intervention.

Per-Protocol (PP) Set: All subjects in the Full Analysis Set not identified as major protocol violations (defined to be protocol violations that may have a significant impact on subject outcomes, i.e., eligibility criteria not met). This population will be clearly defined prior to data analysis.

The primary analysis will be based on the full analysis set. The per-protocol set will be supportive and will be used to assess the robustness of study results. Safety analysis will be based on the full analysis set.

10.4 Statistical Analyses

10.4.1 General Approach

Descriptive statistics will be used to summarize study outcomes. For categorical data, frequency counts and percentages will be provided. For continuous data, descriptive statistics, including sample size, mean, median, standard deviation, and range of values (i.e., minimum and maximum values) will be provided.

All data collected in this study will be provided in subject data listings. Data collected in this study will be reported using summary tables and graphs as appropriate to the data. Descriptive summary statistics (n, mean, median, standard deviation, minimum and maximum) will be calculated for the continuous variables and/or frequencies and percentages will be produced for the categorical variables.

10.4.2 Measures to Minimize Bias: Randomization and Blinding

This study does not include a randomization or blinding component. When screening subjects for the study, the investigators or designee should offer participation to any/all patients who meet the inclusion and exclusion and who completed the prior T-GENVIH-002 study.

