5.1 Inclusion Criteria

1. Patient was a subject in the T-GENVIH-002 study and underwent minimally invasive (i.e., laparoscopic or robotic) surgical abdominal wall reconstruction for a primary hernia repair using Integra Gentrix® Surgical Matrix.
2. Subject has participated in the informed consent process and signed a study-specific informed consent document.
3. Subject is fluent in US English or US Spanish language.
4. Subject is willing to complete an e-consent and phone or in-office visit.

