5.2 Exclusion Criteria

Not applicable.

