5.5 Strategies for Recruitment

A one-off subject phone (call) visit will constitute the source of data and will be collected using a study-specific eCRF delivered via a phone script by the site responsible or their designee(s). Each patient should be included in the study only once. Patient screening will rely on site identification and contact of prior T-GENVIH-002 study subjects (Sponsor remains blinded) and e-consent process. In these cases, every effort should be made to identify every possible eligible patient. For those that are lost to follow up, site may work directly with a Sponsor approved people search service (Sponsor remains blinded). In order to be eligible for the study, patients should meet all of the eligibility criteria.

For subjects who decline an electronic consent collected remotely, an in-office interview and assistance with completing the electronic consent in person with the site study coordinator or their designee(s) will be offered for the convenience of the subjects and to maximize data collection efforts.

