6.1 Schedule of Data Collection

6.1.1 Eligibility/Consent

- The procedures to be completed are:

- ✓ Identification of the full consecutive series of patients who underwent abdominal wall reconstruction for a minimally invasive surgical approach (i.e., laparoscopic or robotic) hernia with Integra® Gentrix® Surgical Matrix from the prior T-GENVIH-002 study and informed consent for those who volunteer to participate.
- ✓ Creation on the CRF of a new case book for each eligible subject. Each created case book assigns the eligible subject with a study number.
- ✓ Completion of Worksheets/ CRFs: Site will transcribe/transmit the below-mentioned patients' data in study CRFs. The patients' data will originate from a direct interview with the subject by the study coordinator.
- The patients' data to be collected are:
 - ✓ Eligibility:
 - Inclusion Criteria: Ensure the subject meets all the inclusion criteria.

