9.3 Endpoint Analysis

Primary, Secondary and Safety Endpoints will be analyzed based on the Visit 1 Questionnaire report.

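### Protocol 10.4.2 ties the offer of participation to completing T-GENVIH-002, which the eligibility criteria do not require; separately, two SAP sections use the enrolled set where safety is otherwise assigned to ITT/FAS

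*Protocol*

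**What the plan says.** **Offer of participation.** Protocol 10.4.2, the section on minimising bias, says that the investigators or their designee "should offer participation to any/all patients who meet the inclusion and exclusion and who completed the prior T-GENVIH-002 study". The first criterion in Protocol 5.1 reads "Patient was a subject in the T-GENVIH-002 study and underwent minimally invasive" repair with the device; the other three cover consent, language and willingness to do the e-consent and visit. Protocol 5.2 on exclusions reads "Not applicable". Protocol 5.5 relies on contacting prior T-GENVIH-002 subjects, says that "every effort should be made to identify every possible eligible patient", and allows a people-search service for those lost to follow-up. Protocol 6.1.1 begins with "Identification of the full consecutive series of patients who underwent abdominal wall reconstruction" by the minimally invasive route. On size, Protocol 10.2 says: "The planned sample size for this study will be approximately 21 treated subjects". SAP 9.3 states: "Primary, Secondary and Safety Endpoints will be analyzed based on the Visit 1 Questionnaire report".

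**Safety set.** Protocol 10.3 assigns safety to the Full Analysis Set (FAS): enrolled, consented, and received study intervention. SAP 7 assigns it to ITT, defined in nearly the same terms except that it speaks of a consent waiver. SAP 9.3.3 puts device deficiencies in the enrolled population. SAP 9.3.4 puts safety in the enrolled population in its first paragraph and in a full analysis population in its second. SAP 7 defines enrolled as all eligible subjects.

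**The concern.** The completion clause adds a condition to the offer that no eligibility text contains. If a site follows it, entry depends on how a patient's follow-up went in the parent study. A patient who withdrew or was lost there is then not approached, has no Visit 1 Questionnaire, and drops out of the recurrence proportion. With about 21 subjects, one or two such patients would matter to a single descriptive percentage.

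The safety-set wording is a separate matter. The SAP names one set in its populations section and another where the tables are specified, so the programmer has to choose the denominator.

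**Working it through.** **The stated figure.** The 21 is a planned count. SAP 8 says that it does not rest on hypothesis testing, and the documents give no rate, precision target or dropout behind it, so there is nothing to reproduce. They also do not say whether 21 is the whole minimally invasive series or the expected participants.

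**Part 1: the texts side by side.**

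| Place | Who is meant | Completion required? |
|---|---|---|
| Protocol 5.1, 5.2 | Was a T-GENVIH-002 subject with laparoscopic or robotic repair; no exclusions | No |
| Protocol 5.5 | Prior subjects, all possible eligible patients, people search for those lost | No |
| Protocol 6.1.1 | The whole consecutive series | No |
| Protocol 10.1, 10.2 | Subjects of the series, on the defined criteria | Not mentioned |
| Protocol 10.4.2 | Those meeting the criteria who also completed T-GENVIH-002 | Yes, for the offer; term undefined |

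**Part 1: scale, illustrative only.** Let N be the series, m the number not approached, c the recurrences among those included and k those among the m. The reported proportion is c/(N − m); the full-series proportion is (c + k)/N. The part left undetermined is at most m/N.

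- N = 21, m = 1: at most 1/21 = 4.8 points. If 21 are participants and one more is left out, 1/22 = 4.5 points.
- N = 21, m = 2: at most 2/21 = 9.5 points. If one of the two already has a recurrence recorded in T-GENVIH-002, (2 − 1)/21 = 4.8 points.
- N = 21, m = 4, c = 2: reported 2/17 = 11.8%; full series 2/21 = 9.5%, 3/21 = 14.3% or 4/21 = 19.0% for k = 0, 1 or 2. The error can go either way.
- m = 0: no effect.

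All values of m, c and k are assumed. The same arithmetic holds for anyone who declines or cannot be reached, so it shows what one missing subject can do and does not measure the effect of this clause.

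**Part 2: do enrolled and ITT differ?** Enrolled requires eligibility; ITT also requires study intervention. The eligibility criteria ask for willingness to complete the visit, not for the visit itself.

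- If study intervention is the interview, as the Protocol synopsis describes it, a consented but uninterviewed subject is enrolled but not in ITT. SAP 9.3.4 and SAP 11 do not say how that subject enters a percentage.
- If it is the device, every eligible subject has received it, and the sets coincide apart from the consent wording. The reference to treated subjects in Protocol 10.2 and SAP 8 leans this way, while Protocol 2.2.4 calls the study noninterventional.

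Assume 21 enrolled and 2 with an event. All enrolled: 2/21 = 9.5%. One not interviewed: 2/20 = 10.0%. Two not interviewed: 2/19 = 10.5%. The largest difference is 10.5 − 9.5 = 1.0 point; under the device reading it is 0.

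**The case against.** The case against part 1 is substantial. The sentence in 10.4.2 is written to prevent selective approach and bars nobody. Eligibility is set in 5.1 and 5.2. Section 5.5 starts from prior subjects and offers a people search for those lost, the group most likely to overlap with non-completers. The words in 5.5 and 6.1.1 concern identifying patients, which is a different step from offering participation. All of this stands, and it limits the point to a clash of wording and intent. It does not remove the clause, which is an operational instruction on whom to approach at screening.

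A reader might infer that non-completers are excluded, or that the recurrence rate will be biased in a known direction. The documents support neither: 10.4.2 does not say *only*, the number of non-completers is not given, and nothing is said about their outcomes. A reader might also take Protocol 10.1 ("Subjects from that consecutive series will be included in the study based on the defined inclusion and exclusion criteria") to make the criteria the sole basis of entry; it does not say so.

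On part 2, one might count three or four rival safety sets. That is too many. ITT and FAS are nearly identical in wording, the SAP's per-protocol definition itself refers to a full analysis set, and the full analysis population in 9.3.4 is probably the same thing under another label. The real mismatch is enrolled against ITT/FAS. The study is descriptive and lists events by subject, so a reader could see who had them.

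**Conclusion.** Both inconsistencies are in the text, and both are low priority.

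1. Protocol 10.4.2 conditions the offer on an undefined completion status that 5.1 and 5.2 do not require and that conflicts with the intent of 5.5 and 6.1.1. The effect is unknown and may be nil. It arises only if there are minimally invasive non-completers and the site applies the clause as a condition; no direction of bias is implied.
2. SAP 9.3.3 and the first paragraph of 9.3.4 use a different set from SAP 7 and Protocol 10.3. The effect is small, at most 1.0 point under the assumed counts, and 0 if study intervention means the device.

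The two parts are independent. A disposition table starting from the identified series would be a useful option, but its absence contradicts nothing and is not part of this point.

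**What to change.** - **Protocol 10.4.2:** delete the completion clause, so that participation is offered to all minimally invasive T-GENVIH-002 subjects who meet 5.1.
- **SAP 7, 9.3.3 and 9.3.4:** use one label and one definition, the Protocol FAS, for endpoints, safety and device deficiencies, replacing both ITT and enrolled. Changing the safety sections alone would leave two labels for what is essentially one set.
- **Protocol 10.3 and SAP 7:** state that study intervention is the Visit 1 interview, or define it otherwise.
- **SAP 7:** replace the consent-waiver wording with informed consent, as in Protocol 5.1 and 10.3; read literally, it makes membership of the set unclear. The same wording in SAP 9.2.1 should follow.

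The cost is a clause and a definition in the protocol and wording edits in the SAP. No new data or analysis is needed. If T-GENVIH-002 had no minimally invasive non-completers, deleting the clause loses nothing.

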10.4.3 Analysis of the Primary Endpoint(s)

The primary endpoint for this study is descriptive statistics of clinically confirmed recurrence of the primary hernia to date, including not previously reported in T-GENVIH-002 study.

10.4.4 Analysis of the Secondary Endpoint(s)

Descriptive statistics will be provided for the following secondary endpoints:

1. Incidence of self-reported recurrence (i.e., bulge) of the primary hernia to date, including not previously reported in T-GENVIH-003 study.
2. Incidence of Surgical Site Occurrences requiring Procedural Intervention (SSOPI) of the primary hernia repair to date, including not previously reported in T-GENVIH-002.
3. Incidence of Surgical Site Occurrences (SSOs) of the primary hernia repair to date (seroma, abscess, dehiscence, hematoma, wound necrosis, ileus, fistula, delayed wound healing), including not previously reported in T-GENVIH-002 study.
4. Incidence of Surgical Site Infections (SSIs) post primary hernia repair to date, including not previously reported in GENVIH-002 study.
5. Incidence of reoperation requirement of the primary hernia repair to date, including not previously reported in GENVIH-002 study.

10.4.5 Safety Analyses

All AEs will be coded using the Medical Dictionary for Regulatory Activities (MedDRA) and presented in by-subject listings. The number and percent of subjects experiencing any AE, any related AE, and discontinuations due to an AE will be tabulated. Treatment-emergent AEs will be tabulated (frequencies and percentages) by Preferred Term (PT) within System Organ Class (SOC). If a subject experiences more than one occurrence of the same AE, and these differ in severity and/or causality, the AE will be tabulated according to the greatest severity and nearest relationship to the device. Deaths and SAEs will be listed should they occur.

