7.3 Reporting Requirements

7.3.1 Reporting of AEs and SAEs

The investigator will determine if there has been a potentially device or procedure related adverse event or potentially device or procedure related serious adverse event. All potentially device or procedure related adverse events and potentially device or procedure related serious adverse events must be reported on the “Adverse Event” form.

Potentially device or procedure related adverse events and potentially device or procedure related serious adverse events will be evaluated and differentiated by:

- Seriousness of the event;
- Causality of the event (in relation to the device or procedure);

- Severity of the event.

All potentially device or procedure related AEs and potentially device or procedure related SAEs must be collected for all enrolled subjects starting from the time of enrollment through the last Follow-up. Each AE must be described as follows:

AE Term: A medically defined diagnosis/symptom. Use the highest level of evidence available.

Level 1: Diagnosis (highest level)

Level 2: Symptoms

Level 3: Signs (lower level)

AE Description: Explain the circumstance of becoming aware of the event, how the subject explained the circumstances surrounding the onset of the event, the underlying cause (the diagnosis), coexisting disease, or other condition or complaint involving the event.

AE Duration: Document by entering the date of onset (start date) and date of resolution (stop date).

AE Causality: Document causal relationship between event and the investigational product and Study Procedure (causally related, possible, probably, not related).

AE Seriousness: Document as serious or not serious.

AE Severity: Document as mild (transient and easily tolerated by the subject), moderate (discomfort and interrupts normal activities), or severe (incapacitating with inability to work or do usual activity).

Action(s) Taken and/or Treatment(s): Document as none, medication, hospitalization, surgical, and/or other. Any prescribed medication should be noted in the subject's medical records and transcribed onto the AE and Concomitant Medications CRFs. If a surgical or invasive procedure is required for an AE, document the procedure on the Invasive Procedure Log.

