9.3.4 Analysis of Adverse Events

The incidence rate of each of the adverse device effects from the follow-up visit will be presented. The incidence of adverse events and serious adverse events will be tabulated (frequencies and percentage of patients) by severity and relationship to device and procedure. The analysis of safety will be performed in the enrolled population.

Descriptive statistics will be provided for safety endpoints by surgical procedure. All safety summaries will be presented for the full analysis population. Adverse Device Events will be coded according to Medical Dictionary for Regulatory Activities (MedDRA) AE coding dictionary. All ADEs will be listed. A summary of the frequency count and percentage of subjects reporting each ADE category will be produced for all reported ADEs and SADEs. Relationship of AE verbatim text to group terms and body systems will also be reported. A listing of withdrawals due to ADEs will be provided. Deaths and SADEs will be listed should they occur.

AE listing includes Onset Date, AE Term, Relation to Device, Relation to Procedure, Pattern, Seriousness (SAE), Severity, Treatment, Medication, Surgical, Outcome, End Date. By subject listings will be provided for each subject reported.

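### Deaths before consent cannot be listed and withdrawals for adverse events can hardly occur, so two planned safety outputs are near-empty by design

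*Protocol*

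**What the plan says.** **Who can be in the data.** Protocol 5.1 requires: "Subject has participated in the informed consent process and signed a study-specific informed consent document". It also requires: "Subject is willing to complete an e-consent and phone or in-office visit". Protocol 10.4.2 directs the offer to patients "who completed the prior T-GENVIH-002 study". The Full Analysis Set in Protocol 10.3 is restricted to consented, enrolled subjects.

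**Where the data come from.** Protocol 5.5: "A one-off subject phone (call) visit will constitute the source of data". Protocol 6.1.1: "The patients' data will originate from a direct interview with the subject by the study coordinator". No relative, proxy, registry or chart source is named for someone who cannot be interviewed. Protocol 7.3.1 collects adverse events for enrolled subjects, from enrolment to the last follow-up.

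**What will be reported.** Protocol 10.4.5: "The number and percent of subjects experiencing any AE, any related AE, and discontinuations due to an AE will be tabulated". The same section plans a listing of deaths and SAEs. SAP 9.3.4: "A listing of withdrawals due to ADEs will be provided. Deaths and SADEs will be listed should they occur". The SAP's disposition table (9.2.1) starts with subjects who have consented.

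**What the results are for.** Protocol 3.1 says the investigation will confirm safety and performance in minimally invasive cases and identify side-effects that are unknown or were not reported before.

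**The concern.** The study looks back over a period that ends today but admits only people who are alive today and agree to talk. Anyone who died after T-GENVIH-002 stopped collecting data is outside every analysis set, so the listing that should show the gravest outcome cannot show it. The discontinuation row has a different fault. The device was implanted before the study began, the study gives no treatment, and its only activity after consent is one interview. There is almost nothing to discontinue from.

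At stake is what the safety section of the report can bear. An empty death listing and a zero discontinuation row, printed without comment, carry almost no information about the cohort. Nothing in either document tells the reader so.

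**Working it through.** **1. Route from an event to the output.**

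| Event | Can the subject enter an analysis set? | Can it be listed or tabulated? |
|---|---|---|
| Death during T-GENVIH-002 | No | No; it belongs to that study's own reporting |
| Death after the last T-GENVIH-002 data collection, before consent | No: no consent, no interview | No |
| Death between consent and the interview | Yes | Yes |
| Non-fatal event before consent, subject interviewed | Yes | Yes as an AE or SAE; no as a cause of withdrawal |
| AE between consent and the interview leading to withdrawal | Yes | Yes |

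The window that can fill the death listing and the withdrawal outputs is thus consent to interview. The Table 1 footnote in Protocol 1.2 allows activities on separate days, so the window can be zero days or longer. The whole study lasts about 3 months (Protocol 5.4), which bounds it.

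**2. Is there another route?** SAP 9.3.4 names the enrolled population for safety, but SAP 7 defines that population by the eligibility criteria, which include consent. SAP 9.2.1 counts from consent onward. Protocol 8 has the site complete an exit form for people it cannot reach, and SAP 9.2.7 summarises exit type. Neither mentions vital status, and Protocol 6.1.5 describes the form as being for enrolled subjects.

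**3. Size.** The plan has no figure to reproduce: about 21 subjects are planned (Protocol 10.2, SAP 8), with no hypothesis and no event rate. The simplest illustration treats 21 as the size of the series and assumes the number of deaths: 1/21 = 4.8%; 2/21 = 9.5%.

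To compare the two windows, assume all-cause yearly mortality h of 1%, 3% or 5% and a window of length t. Neither the rates nor the longer windows are in the documents. With p = 1 − exp(−h·t), the chance of at least one death among 21 is 1 − (1 − p)^21. Worked once: for h = 1% and t = 2 years, p = 1 − exp(−0.02) = 0.0198; expected deaths are 21 × 0.0198 = 0.42; the chance is 1 − 0.9802^21 = 34%.

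| Window | h = 1% | h = 3% | h = 5% |
|---|---|---|---|
| 1 day, consent to interview | 0.06% | 0.17% | 0.29% |
| 14 days, consent to interview | 0.8% | 2.4% | 3.9% |
| 3 months, the outer bound | 5.1% | 14.6% | 23.1% |
| 2 years, assumed gap before consent | 34% | 72% | 88% |
| 5 years, assumed gap before consent | 65% | 96% | 99% |

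The first three rows are what the plan can list; the last two are what it cannot.

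**4. A true zero would also be weak evidence.** With no selection at all, 0 events in 21 has an exact two-sided 95% upper limit of 1 − 0.025^(1/21) = 16.1%.

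**The case against.** The case on the other side is substantial, and several parts of it stand.

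- **Surgical consequences are already reported.** A reader might infer that surgical revision because of an adverse event goes untabulated. It does not: reoperation and SSOPI are secondary endpoints whose proportions are presented (SAP 3.2 and 9.3.2), and the AE listing in SAP 9.3.4 has a surgical column, matching the action-taken field in Protocol 7.3.1 ("Document as none, medication, hospitalization, surgical, and/or other"). A new row for events leading to reoperation or removal would largely repeat these outputs. This stands.
- **Unrelated deaths are out of scope.** Protocol 7.2.1 and 7.3.1 require only events related, or potentially related, to the repair or the device. The 4.8% and 9.5% are all-cause figures, so they cannot be read as missed safety signals. This stands for deaths known to be unrelated. Protocol 7.2.3 classes events whose relatedness cannot be assessed as possible, so a death of unknown cause is not plainly out of scope.
- **The output is not exactly zero.** A reader might infer that nothing could ever be listed. The gap between consent and visit rules that out; near-empty is the right description.
- **The exit form might record a death.** Its categories are not in the documents, so this cannot be excluded, but nothing commits to it.
- **The SAP speaks of a consent waiver** (7 and 9.2.1), which could in principle admit deceased subjects. But SAP 5 says patients will give consent, and SAP 9.3 analyses the interview questionnaire. The wording should be reconciled; it does not supply a route.
- **Survivor selection is inherent in consented follow-up**, and there is no mortality endpoint. True, and it is why the remedy is a denominator and a caveat, not a redesign.

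**Conclusion.** The point holds as a matter of structure. Deaths between the last T-GENVIH-002 data collection and consent cannot appear in the planned listings, and the AE-discontinuation table and withdrawal listing can capture only what happens between consent and the interview. As they stand, these outputs do not support the stated aim of confirming safety.

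No magnitude follows from the documents: mortality, time since T-GENVIH-002 and the consent-to-interview gap are all unstated, and every percentage in the table of windows rests on assumed values.

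A reader might go further and infer that the plan hides a known share of serious outcomes, or that it presents an empty listing as a favourable result. The documents support neither. No deaths are reported in them, the listings are conditional on deaths occurring, and a favourable reading would be the reader's own. Non-fatal events, including serious ones, can still be reported by survivors, and no primary or secondary endpoint definition is affected. This is a cheap improvement to the safety reporting.

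**What to change.** 1. **SAP 9.2.1:** start disposition from the full minimally invasive T-GENVIH-002 series, and give aggregate, de-identified counts of subjects known deceased, unreachable, declined and interviewed. The site already identifies the full series (Protocol 6.1.1) and contacts and traces its members (Protocol 5.5 and 8).
2. **Protocol 10.4.5 and SAP 9.3.4:** show the number known deceased beside the adverse event tables, and state that the AE and death outputs describe participating survivors only.
3. **Same sections:** delete the AE-discontinuation row and the listing of withdrawals due to device effects as inapplicable. No replacement row is needed.

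The cost is a few counts from the site's contact log and a short change of wording; no new visit or form is required. Vital status and cause of death will be incomplete, so the deceased count is a minimum. IRB agreement may be needed for the counts. Dates of death and relatedness assessments for people who did not consent would be a larger and more debatable extension, and are not proposed here.
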